## 5.4. Withdrawal/Stopping Criteria

### WITHDRAWAL CRITERIA(Specific for Group A ONLY)

1. A subject will be withdrawn from the study, if they demonstrate an excessive or adverse reaction to the photoprovocation, as judged by the Investigator after discussion with the medical monitor.

The following actions must be taken in relation to a subject who fails to attend the clinic for a required study visit:

- The site must attempt to contact the subject and re-schedule the missed visit as soon as possible.
- The site must counsel the subject on the importance of maintaining the assigned visit schedule and ascertain whether or not the subject wishes to and/or should continue in the study. In case a subject withdraws from study they should be encouraged to continue contraception for 28 days.
- In cases where the subject is deemed 'lost to follow up', the investigator or designee must make every effort to regain contact with the subject (where possible, 3 telephone calls and if necessary a certified letter to the subject's last known mailing address or local equivalent methods). These contact attempts should be documented in the subject's medical record.
- Should the subject continue to be unreachable, only then will he/she be considered to have withdrawn from the study with a primary reason of "Lost to Follow-up".

A subject may withdraw from study treatment at any time at his/her own request, or may be withdrawn at any time at the discretion of the investigator for safety, behavioural or administrative reasons. If a subject withdraws from the study, he/she may request destruction of any samples taken, and the investigator must document this in the site study records.

At the time a subject withdraws, every effort should be made to conduct assessments stipulated at the follow-up visit, as per the time & events tables, Section 7.1.

If subjects prematurely discontinue the study, additional replacement subjects may be enrolled at the discretion of the Sponsor in consultation with the investigator.

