
 • Reporting for tables, figures and formal statistical analyses : 
 • Planned time relative to dosing will be used in figures, summaries, statistical analyses and calculation of any derived parameters, unless otherwise stated. • The impact of any major deviation from the planned assessment times and/or scheduled visit days on the analyses and interpretation of the results will be assessed as appropriate. • Reporting for Data Listings: 
 • Planned and actual time relative to study drug dosing will be shown in listings (Refer to IDSL Statistical Principle 5.05.1). • Unscheduled or unplanned readings will be presented within the subject's listings. • Visits outside the protocol defined time-windows (i.e. recorded as protocol deviations) will be included in listings but omitted from figures, summaries and statistical analyses. 	
Unscheduled Visits	

 • Unscheduled visits will not be included in summary tables. • Unscheduled visits will not be included in figures. • All unscheduled visits will be included in listings. 	
Descriptive Summary Statistics	
Continuous Data	Refer to IDSL Statistical Principle 6.06.1
Categorical Data	N, n, frequency, %
Reporting of Pharmacokinetic Concentration Data	
Descriptive Summary Statistics	Refer to IDSL Statistical Principle 6.06.1 Assign zero to NQ values (Refer to GUI_51487 for further details)
Reporting of Pharmacokinetic Parameters	
Descriptive Summary Statistics (Log Transformed)	N, n, geometric mean, 95% CI of geometric mean, standard deviation (SD) of logged data and between geometric coefficient of variation (CV _{b/w} (%)) will be reported. [1] CV _b (%) = $\sqrt{(\exp(SD^2) - 1) * 100}$ (SD = SD of log transformed data) [2] CV _w (%) = $\sqrt{(\exp(MSE) - 1) * 100}$ (MSE = mean square error from mixed effect model of loge-transformed data).
Graphical Displays	

 • Refer to IDSL Statistical Principals 7.01 to 7.13. 	

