11.3. Appendix 3: Derived and Transformed Data

11.3.1. General

Multiple Measurements at One Time Point

 Mean of the measurements will be calculated and used in any derivation of summary statistics but if listed, all data will be presented. Subjects having both High and Low values for Normal Ranges at any post-baseline visits for safety parameters will be counted in both the High and Low categories of "Any visit post-baseline" row of related summary tables. This will also be applicable to relevant Potential Clinical Importance summary tables.
Study Day

 Calculated as the number of days from randomisation date : 
 Ref Date = Missing → Study Day = Missing Ref Date < Randomisation Date → Study Day = Ref Date – Randomisation Date Ref Date ≥ Randomisation Date → Study Day = Ref Date – (Randomisation Date) + 1

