11.4. Appendix 4: Premature Withdrawals & Handling of Missing Data

11.4.1. Premature Withdrawals

Element	Reporting Detail
General	
 Subject study completion (i.e. as specified in the protocol) was defined as subject who receives at least 25 days of study drug and completes the end of treatment biopsy and assessment. Withdrawn subjects may be replaced in the study. All available data from subjects who were withdrawn from the study will be listed and all available planned data will be included in summary tables and figures, unless otherwise specified.

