11.8.5. Safety Tables

Safety : Tables					
No.	Population	IDSL / TST ID / Example Shell	Title	Programming Notes	Deliverable [Priority]
Adverse Events					
2.1.	Safety	CP_AE1p	Summary of All Adverse Events by System Organ Class (Group B-Natural Lesions)	Only Total adverse events will be summarised.	SAC
2.2.	Safety	CP_AE1p	Summary All Drug-Related Adverse Events by System Organ Class (Group B-Natural Lesions)	Only Total adverse events will be summarised.	SAC

Safety : Tables					
No.	Population	IDSL / TST ID / Example Shell	Title	Programming Notes	Deliverable [Priority]
Serious and Other Significant Adverse Events					
2.3.	Safety	CP_AE1p	Summary of Serious Adverse Events by System Organ Class (Group B-Natural Lesions)	Only Total adverse events will be summarised.	SAC
2.4.	Safety	CP_AE1p	Summary of Adverse Events Leading to Withdrawal from Study / Permanent Discontinuation of Study Treatment by Overall Frequency (Group B-Natural Lesions)	Only Total adverse events will be summarised.	SAC
Laboratory: Chemistry					
2.5.	Safety	LB1	Summary of Chemistry Changes from Baseline (Group B-Natural Lesions)	Treatment column will not be displayed.	SAC
2.6.	Safety	LB3	Summary of Emergent Chemistry Results Relative to Normal Range (Group B-Natural Lesions)	Treatment columns will be replaced by one 'Part B' column	SAC
Laboratory: Hematology					
2.7.	Safety	LB1	Summary of Hematology Changes from Baseline (Group B-Natural Lesions)	Includes baseline values. Treatment column will not be displayed.	SAC
2.8.	Safety	LB3	Summary of Emergent Hematology Results Relative to Normal Range (Group B-Natural Lesions)	As notes for Chemistry T2.12.	SAC
Laboratory: Urinalysis					
2.9.	Safety	LB1	Summary of Urine Concentration Changes from Baseline (Group B-Natural Lesions)	Includes Baseline values. Treatment column will not be displayed.	SAC
2.10.	Safety	LB2	Summary of Emergent Urinalysis Dipstick Results (Group B-Natural Lesions)	As above for Chemistry, using dipstick categories.	SAC
Laboratory: Hepatobiliary (Liver)					
2.11.	Safety	LIVER1	Summary of Liver Monitoring/Stopping Event Reporting (Group B-Natural Lesions)	Treatment columns will be replaced by one 'Part B' column	SAC

Safety : Tables					
No.	Population	IDSL / TST ID / Example Shell	Title	Programming Notes	Deliverable [Priority]
2.12.	Safety	LIVER10	Summary of Subjects Meeting Emergent Hepatobiliary Laboratory Abnormality Criteria (Group B-Natural Lesions)	Treatment columns will be replaced by one 'Part B' column	SAC

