ECG					
2.13.	Safety	EG1	Summary of ECG Findings (Group B-Natural Lesions)	Treatment columns will be replaced by one 'Part B' column	SAC
2.14.	Safety	CP_EG11	Summary of Maximum Emergent QTc Values by Category (Group B-Natural Lesions)	Treatment columns will be replaced by one 'Part B' column	SAC
2.15.	Safety	EG2	Summary of Change from Baseline in ECG Values by Visit (Group B-Natural Lesions)	Note: IDSL shell in development. Includes Baseline values. Treatment columns will be replaced by one 'Part B' column	SAC
2.16.	Safety	CP_EG12	Summary of Maximum Change from Baseline in QTc Values by Category (Group B-Natural Lesions)	Treatment columns will be replaced by one 'Part B' column	SAC
Vital Signs					
2.17.	Safety	VS1	Summary of Change from Baseline in Vital Signs by Visit (Group B-Natural Lesions)	Treatment column will not be displayed.	SAC
2.18.	Safety	VS3	Summary of Emergent Vital Signs Results Relative to Normal Range (Group B-Natural Lesions)	Treatment columns will be replaced by one 'Part B' column	SAC
Local Tolerability					
2.19.	Safety	SAFE_T1	Summary (Absolute and Change from Baseline) of Mean irritation score assessment – (Group B-Natural Lesions)		SAC
2.20.	Safety	SAFE_T2	Assessment of Maximum Dermal Reactions and Response (Group B-Natural Lesions)		SAC

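### SAP 11.2.3 keeps unscheduled visits out of every summary table, so the worst-case liver table, and more narrowly the other emergent and maximum safety tables, can miss a value found off schedule

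*SAP*

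**What the plan says.** SAP 11.2.3 gives one rule for unscheduled visits: "Unscheduled visits will not be included in summary tables". It applies the same rule to figures and keeps these visits for listings. Visits outside the protocol windows, where recorded as deviations, "will be included in listings but omitted from figures, summaries and statistical analyses". For patients who withdraw, SAP 11.4.1 says that "all available planned data will be included in summary tables and figures, unless otherwise specified".

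Beside its by-visit tables, SAP 11.8.5 plans several Group B displays of a worst or any-time result:

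- emergent chemistry, haematology, urinalysis and vital-sign results (Tables 2.6, 2.8, 2.10, 2.18);
- the liver table 2.12 ("Summary of Subjects Meeting Emergent Hepatobiliary Laboratory Abnormality Criteria (Group B-Natural Lesions");
- the QTc tables 2.14 ("Summary of Maximum Emergent QTc Values by Category (Group B-Natural Lesions") and 2.16 (largest change from baseline).

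The programming notes for these tables deal with layout or refer to another table's notes. None mentions unscheduled readings.

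On the protocol side, section 7.4.7 has clinically significant laboratory results re-tested until they settle. Section 12.2 asks for repeat liver chemistry within 24 hours or 24 to 72 hours of a stopping event, then once or twice weekly. It also asks for weekly visits when a raised ALT is being watched on treatment. Section 7.4 allows extra safety time points.

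**The concern.** Dropping unscheduled visits from by-visit summaries is good practice, because it keeps each column tied to a common time. A table headed maximum or emergent has a different job: it should report the worst reading a patient had, whenever it was taken. Run as written, such a table can leave out the value it exists to show.

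Laboratory tests, vital signs and ECG are components of the primary endpoint, and the primary analysis is a descriptive summary of them, so these tables are the main safety result. The liver displays could also disagree. A patient who reaches a stopping criterion is recorded on the liver event CRF, and on an SAE form if the event is serious, and so can enter Table 2.11 or 2.3. Table 2.12, which is defined by laboratory criteria, would not show the qualifying result if it came from an unscheduled visit.

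**Working it through.** **1. Is there an exception anywhere?** Three places could hold one.

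- SAP 11.3.1 says "Subjects having both High and Low values for Normal Ranges at any post-baseline visits for safety parameters will be counted" in both categories of the any-visit row. This settles how to count a patient who is both High and Low. It does not mention unscheduled visits.
- The notes to Tables 2.6 to 2.18 are silent.
- SAP 11.2.3 applies the sponsor's IDSL reporting standards except where the SAP states otherwise. Here it does, so those standards do not clearly restore the readings.

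**2. Scheduled readings against required repeats.** Group B post-baseline schedule, from protocol 7.1.3 and SAP 11.1.4 (the extracted tables have lost a column in some rows; the last mark for laboratory tests and ECG is read as follow-up):

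| Assessment | Scheduled after baseline | Number |
|---|---|---|
| Laboratory tests | Day 14, Day 28, follow-up (Days 43 to 56) | 3 |
| Vital signs | Day 14, Day 28 | 2 |
| ECG | Day 14, follow-up (Days 43 to 56) | 2 |

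Suppose ALT is raised on Day 14 and followed weekly. The repeats fall on Days 21, 28, 35 and 42. Only Day 28 is a scheduled laboratory day, so three of the four repeats are off schedule. The two ECGs are 43 − 14 = 29 to 56 − 14 = 42 days apart, so an ECG on Days 15 to 42 would be an added one.

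**3. What each table can lose.**

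- Table 2.12: a later ALT peak, or ALT and bilirubin meeting a joint criterion for the first time, at an unscheduled visit. The Day 14 rise itself is still counted.
- Tables 2.6, 2.8 and 2.10: a first abnormality in a different analyte on a repeat panel, or one found at an added safety visit.
- Table 2.18: a first abnormality at an added safety visit only.
- Tables 2.14 and 2.16: a higher QTc only if an ECG is taken at an added visit.

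**4. Size of one missed patient.** Protocol 9.2.1 uses a flat Beta(1,1) prior, so with x events in n patients the upper limit is the 97.5th percentile of Beta(1 + x, 1 + n − x). The protocol's Group B figures for n = 15 reproduce:

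| Events | Posterior | Computed | Stated |
|---|---|---|---|
| 0 | Beta(1,16) | 20.6% | 21% |
| 1 | Beta(2,15) | 30.2% | 0.30 |
| 2 | Beta(3,14) | 38.4% | 38% |

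If the only patient with a given abnormality shows it at an unscheduled visit, the table reads 0/15 (20.6%) instead of 1/15 (30.2%). If one of two is missed, it reads 1/15 (30.2%) instead of 2/15 (38.4%). The counts are illustrative.

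**5. Separate point: AE stop dates.** Illustrative dates: last dose 28 March, onset 5 April, stop recorded as April with no day. SAP 11.4.2.1 caps the imputed stop at the end of treatment, 28 March. Stop − onset + 1 is then −8 + 1 = −7 days. SAP 11.4.2.2 has no cap and gives 30 April: 25 + 1 = 26 days. The two rules disagree, and the first can place the stop before the onset.

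**The case against.** The strongest reply is that the reach is small, and much of it stands.

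- **Triggers follow an abnormality.** The laboratory repeats begin after an abnormal value. If that value came at a scheduled post-baseline visit, the patient is already in the table. In the normal-range tables a patient who is High on Day 14 stays High whatever the later peak, so peak size matters mainly for Table 2.12.
- **ECG and vital signs.** Beyond the general permission in protocol 7.4, no specific trigger for an unscheduled ECG or vital-sign visit is given. The confirmatory ECGs in protocol 5.4.5 are taken close together and are most naturally replicates. For those the SAP is settled: "Mean of the measurements will be calculated and used in any derivation of summary statistics". For example, QTcF readings of 510, 480 and 470 msec at one time point enter as 1460/3 = 486.7 msec.
- **Wording by visit.** Dosing and tolerability checks run through Day 28, so a blood draw added to one of those visits is not plainly excluded. The SAP does not say, which is itself a reason to clarify.
- **Mitigation.** Unscheduled readings are listed. Listings 23 to 33 cover laboratory, ECG and vital-sign values of potential clinical concern or importance and can be read case by case in about 15 patients. AE tables do not depend on visits. The IDSL shells that govern these tables are not shown.

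A reader might also infer that patients who leave early lose all post-baseline safety data from the tables, since only planned data are admitted. The documents do not support that. Protocol 5.4 says "At the time a subject withdraws, every effort should be made to conduct assessments stipulated at the follow-up visit", and footnote a on the follow-up column, in both the protocol and SAP schedules, requires the listed procedures at premature withdrawal. Those assessments are part of the schedule and read naturally as planned.

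**Conclusion.** The concern holds in a limited form. SAP 11.2.3 is unqualified, nothing in the documents restores unscheduled readings to the worst-case tables, and the protocol requires off-schedule laboratory repeats. The clearest exposure is Table 2.12. Tables 2.6, 2.8, 2.10 and 2.18 are exposed to a first abnormality found off schedule, and Tables 2.14 and 2.16 only through an ECG at an added visit.

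It would be wrong to infer that abnormal results are lost, or that first abnormalities would routinely go uncounted. The values stay in the listings, an abnormality seen at a scheduled visit is counted, and the frequency of the problem cannot be derived from the documents. No formal test is affected. What is at risk is a table milder than the listings behind it, or two liver tables that disagree. One patient in 15 moves the upper limit by about ten percentage points (30.2% to 20.6%).

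This rests on three assumptions: the unseen IDSL shells do not override the SAP, the follow-up column is read correctly, and Group B has its planned 15 patients.

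The AE stop-date conflict is real but separate and minor. It affects derived duration only, not AE counts.

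**What to change.** In SAP 11.2.3 add one sentence, worded by reading and not by visit: *Unscheduled and out-of-window post-baseline readings are excluded from by-visit summaries but included in the maximum, any-visit-post-baseline, emergent and hepatobiliary-criteria tables (2.6, 2.8, 2.10, 2.12, 2.14, 2.16, 2.18), after averaging replicates at one time point as in 11.3.1.*

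In SAP 11.4.1 note that the withdrawal assessments required by footnote a of the Time and Events table count as planned data, and align that wording with the new sentence.

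Separately, merge the AE parts of 11.4.2.1 and 11.4.2.2 into one rule. Keep the query to data management and the provision for a missing month, drop the cap at the end of treatment, and never impute a stop before the onset. In the example this gives 30 April and 26 days.

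The cost is a few SAP sentences and minor programming. The readings are already collected and listed, so no new data are needed.

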11.3. Appendix 3: Derived and Transformed Data

11.3.1. General

Multiple Measurements at One Time Point

 Mean of the measurements will be calculated and used in any derivation of summary statistics but if listed, all data will be presented. Subjects having both High and Low values for Normal Ranges at any post-baseline visits for safety parameters will be counted in both the High and Low categories of "Any visit post-baseline" row of related summary tables. This will also be applicable to relevant Potential Clinical Importance summary tables.
Study Day

 Calculated as the number of days from randomisation date : 
 Ref Date = Missing → Study Day = Missing Ref Date < Randomisation Date → Study Day = Ref Date – Randomisation Date Ref Date ≥ Randomisation Date → Study Day = Ref Date – (Randomisation Date) + 1

11.3.2. Study Population

Demographics
Age

 GSK standard IDSL algorithms will be used for calculating age where birth date will be imputed as follows: 
 Any subject with a missing day will have this imputed as day '15'. Any subject with a missing date and month will have this imputed as '30th June'. Birth date will be presented in listings as 'YYYY'.
Body Mass Index (BMI)

 Calculated as Weight (kg) / Height (m)²

Extent of Exposure

 Number of days of exposure to study cream will be calculated based on the formula: Duration of Exposure in Days = Treatment Stop Date – (Treatment Start Date) + 1 Subjects who were randomised but did not report a treatment start date will be categorised as having zero days of exposure. Exposure data on a day is recorded in the eCRF in the following manner: 
 Weight of container and ancillary kit BEFORE application (A) Weight of container and ancillary kit AFTER application (B) Location of cream application, where all locations that apply are ticked (C) 
This means that the weight of cream that was applied on that day (calculated as B-A) is the total dose of cream, with part of the total dose of cream applied to each of all the body locations (C) that are ticked.
 The cumulative dose of cream will be based on the formula:

Extent of Exposure

Cumulative Dose = Sum of (Number of Days x Total Daily Dose of cream)

- If there are any treatment breaks during the study, exposure data will be adjusted accordingly.

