6. STUDY POPULATION ANALYSES

6.1. Overview of Planned Analyses

The study population analyses will be based on the Safety population, unless otherwise specified.

Table 2 provides an overview of the planned study population analyses, with full details of data displays being presented in [Appendix 8](#): List of Data Displays.

Table 2 Overview of Planned Study Population Analyses

Endpoint / Parameter / Display Type	Data Displays Generated		
	Table	Figure	Listing
Subject Disposition			
Subject Disposition	Y		
Reasons for Screen Failure	Y		Y
Subjects by Country and Centre	Y		
Reasons for Subject Withdrawal			Y
Subjects for Whom the Treatment Blind was Broken			Y
Planned and Actual Treatments			Y
Protocol Deviations			
Important Protocol Deviations	Y		Y
Subjects with Inclusion/Exclusion Criteria Deviations			Y [1]
Populations Analysed			
Study Populations and Exclusions	Y		
Subjects Excluded from Any Population			Y
Demographic and Baseline Characteristics			
Demographic Characteristics	Y		Y
Race and Racial Combinations	Y		Y [2]
Race and Racial Combination Details	Y		
Prior and Concomitant Medications			
Current/Past Medical Conditions	Y		Y
Concomitant Medications	Y		Y
Type of CLE	Y		Y
Exposure and Treatment Compliance			
Exposure to Study Treatment	Y		Y

NOTES :

- Y = Yes display generated.

[1] Listing also includes analysis population exclusions.

[2] Listing of race.

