11.8.4. Study Population Tables

Study Population Tables					
No.	Population	IDSL / TST ID / Example Shell	Title	Programming Notes	Deliverable [Priority]
Subject Disposition					
1.1.	Safety	CP_ES1p	Summary of Subject Disposition (Group B-Natural Lesions)		SAC
1.2.	All Screened	ES6	Summary of Reasons for Screen Failure (Group A- PV lesions)		SAC
1.3.	All Screened	ES6	Summary of Reasons for Screen Failure (Group B-Natural Lesions)		SAC
1.4.	Safety	NS1	Summary of Number of Subjects by Country and Centre (Group B-Natural Lesions)		SAC
Protocol Deviation					
1.5.	Safety	DV1	Summary of Important Protocol Deviations (Group B-Natural Lesions)		SAC
Population Analysed					
1.6.	All Screened	SP1	Summary of Study Populations and Exclusions (Group A- PV lesions)		SAC
1.7.	All Screened	SP1	Summary of Study Populations and Exclusions (Group B-Natural Lesions)		SAC

Study Population Tables					
No.	Population	IDSL / TST ID / Example Shell	Title	Programming Notes	Deliverable [Priority]
Demographic and Baseline Characteristics					
1.8.	Safety	DM3	Summary of Demographic Characteristics (Group B-Natural Lesions)	Include BMI	SAC
1.9.	Safety	DM5	Summary of Race and Racial Combinations (Group B-Natural Lesions)		SAC
1.10.	Safety	DM6	Summary of Race and Racial Combination Details (Group B-Natural Lesions)		SAC
Prior and Concomitant medications					
1.11.	Safety	MH1, MH4	Summary of [Current/Past] Medical Conditions (Group B-Natural Lesions)		SAC
1.12.	Safety	CM1	Summary of Concomitant Medications (Group B-Natural Lesions)		SAC
1.13.	Safety	SAFE_T3	Summary of Type of CLE (Group B-Natural Lesions)	Obtained from medical conditions page in eCRF. Under Disease Diagnosis – 2. Disease characteristics.	SAC
Exposure and Treatment Compliance					
1.14.	Safety	EX1	Summary of Weight of Study Cream Applied (Group B-Natural Lesions)	See Section 11.3.2 regarding total daily dose of cream; label first row as "Daily Weight of Cream (g)" with following footnote: "Note: Daily Dose refers to the one lesion that either active or placebo treatment is applied to; Label second row as "Cumulative Weight of Cream (g)".	SAC

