11.8.12. ICH Listings

ICH : Listings					
No.	Population	IDSL / TST ID / Example Shell	Title	Programming Notes	Deliverable [Priority]
Subject Disposition					
1.	PV Failures	ES7	Listing of Reasons for Screen Failure (Group A- PV lesions)		SAC
2.	All Screened	ES7	Listing of Reasons for Screen Failure (Group B-Natural Lesions)		SAC
3.	Safety	ES2	Listing of Reasons for Study Withdrawal (Group B-Natural Lesions)		SAC
4.	Safety	BL1 / BL2	Listing of Subjects for Whom the Treatment Blind was Broken (Group B-Natural Lesions)		SAC
5.	Safety	CP_RD1x	Listing of Planned and Actual Treatments (Group B-Natural Lesions)		SAC
Protocol Deviations					
6.	Safety	DV2	Listing of Important Protocol Deviations (Group B-Natural Lesions)		SAC
7.	Safety	IE3	Listing of Subjects with Inclusion/Exclusion Criteria Deviations (Group B-Natural Lesions)		SAC
Populations Analysed					
8.	All Screened	SA3a	Listing of Subjects Excluded from Any Population (Group B-Natural Lesions)		SAC
Demographic and Baseline Characteristics					
9.	Safety	DM2	Listing of Demographic Characteristics (Group B-Natural Lesions)	Include BMI	SAC
10.	Safety	DM9	Listing of Race (Group B-Natural Lesions)		SAC

ICH : Listings					
No.	Population	IDSL / TST ID / Example Shell	Title	Programming Notes	Deliverable [Priority]
Medical History					
11.	Safety	MH2	Listing of Medical History (Group B-Natural Lesions)		SAC
Prior and Concomitant Medications					
12.	Safety	CP_CM3	Listing of Concomitant Medications (Group B-Natural Lesions)		SAC
Exposure and Treatment Compliance					
13.	Safety	EX3	Listing of Weight of Study Cream Applied (Group B-Natural Lesions)	If applicable adapt to study data See Section 11.3.2 regarding total daily dose of cream i.e. each subject to have one row per day, with weight of cream listed (the total weight calculated from the weight before and after application), column labelled as "Weight of Cream (g)" and each body location/side listed together on that single row.	SAC
Adverse Events					
14.	Safety	CP_AE8	Listing of All Adverse Events (Group B-Natural Lesions)	No treatment heading.	SAC
15.	PV failures	CP_AE8	Listing of All Adverse Events for subjects that were PV failures (Group A-PV Lesions)	No treatment heading.	SAC
16.	Safety	AE7	Listing of Subject Numbers for Individual Adverse Events (Group B-Natural Lesions)	Treatment column will not be displayed.	SAC

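### SAP 11.3.2 calculates cream applied as the after-weight minus the before-weight, so daily and cumulative cream weights come out negative

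*SAP*

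**What the plan says.** Protocol 4.5 has the cream weighed before and after it is applied, but gives no formula. The formula is in SAP 11.3.2, under Extent of Exposure. It describes two eCRF weights, "Weight of container and ancillary kit BEFORE application (A" and "Weight of container and ancillary kit AFTER application (B", where A and B are the labels for the two records. It then gives the daily derivation: "This means that the weight of cream that was applied on that day (calculated as B-A) is the total dose of cream". The cumulative rule follows: "Cumulative Dose = Sum of (Number of Days x Total Daily Dose of cream".

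Two displays use these values. SAP 6.1 (Table 2) plans one table and one listing for "Exposure to Study Treatment". In Appendix 8 these are Table 1.14 and Listing 13, both for Group B. The programming note for Table 1.14 says "See Section 11.3.2 regarding total daily dose of cream", and asks for a daily row and a cumulative row in grams. The note for Listing 13 also points to 11.3.2. It adds only that the total comes from the weights before and after application, without saying which is subtracted from which.

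**The concern.** The object on the scale is the container with its kit. It loses mass when cream is taken out, so the amount applied is the before-weight minus the after-weight, A-B. The SAP has the two terms reversed.

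What is at stake is the exposure display. Table 1.14 and Listing 13 are the only planned summaries of how much cream was applied. Programmed literally, the table would show negative grams for every subject who used cream. Its minimum and maximum would also change places, which is the same sign flip seen again and not a second error. Alternatively, a programmer would correct the formula without a record, and the program would then differ from the SAP.

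**Working it through.** **Inputs**

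- A: weight of container and kit before application (SAP 11.3.2).
- B: weight of container and kit after application (SAP 11.3.2).
- Daily rule: B-A (SAP 11.3.2).
- Cumulative rule: sum over days of the total daily dose (SAP 11.3.2).
- Maximum cream at any time point: 10 mg/cm² over 90 cm² (Protocol 4.5).
- Duration: 28 once-daily applications (Protocol 4.2).

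**Step 1. The protocol's own figure.** 10 mg/cm² × 90 cm² = 900 mg of cream, and 1% of 900 mg is 9 mg of drug. Both match Protocol 4.5. This is the only cream weight in the documents; the B-A rule itself has no worked example.

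**Step 2. Sign of the daily rule.** Let d grams leave the container. Then B = A - d, so B - A = (A - d) - A = -d. The starting weight A cancels, so the result does not depend on the size of the container. If no cream is used, d = 0 and the rule gives 0. On every other day it gives a negative number.

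**Step 3. Illustration.** The 0.9 g row uses the protocol maximum. The 0.1 g and 0.5 g rows are assumed values, included to show that the sign does not depend on the amount. The cumulative column assumes the same amount on all 28 days.

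| Cream used per day | Daily, B-A as written | Daily, A-B | 28-day total, B-A | 28-day total, A-B |
|---|---|---|---|---|
| 0.1 g | -0.1 g | +0.1 g | -2.8 g | +2.8 g |
| 0.5 g | -0.5 g | +0.5 g | -14.0 g | +14.0 g |
| 0.9 g | -0.9 g | +0.9 g | -25.2 g | +25.2 g |

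For example, 28 × (-0.9 g) = -25.2 g.

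**Step 4. Does anything else correct it?** No. Protocol 4.5 gives no direction of subtraction. Table 1.14 sends the programmer back to 11.3.2. Listing 13 does the same and names the two weights without a direction. Neither document calls for an absolute value or for A-B.

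**Step 5. What else uses the formula?** Duration of exposure in SAP 11.3.2 is computed from treatment dates. The non-compartmental PK parameters listed in SAP 8.2.3 (Table 8) contain no dose term. The IFN mRNA models in SAP 8.3.2 do not include cream weight, and none of the analysis populations in SAP Section 4 is defined by it.

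**The case against.** The best defence is that this is a transposed pair of letters with an obvious intent. The SAP calls the quantity the weight of cream applied, the displays carry the same title, and a negative weight is impossible. Anyone running the first output would see it. The magnitudes are intact, so nothing is lost. This stands as far as severity goes: the point cannot be more than minor. It does not make the text right, because 11.3.2 is the only operative formula and has to be overridden to get a sensible result.

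A second objection concerns Listing 13. Its note opens with "If applicable adapt to study data" and gives no direction of subtraction, so the negative sign is less firmly fixed there than in Table 1.14. That is fair. The sign reaches the listing only through its reference to 11.3.2.

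Three stronger readings are tempting, and the documents support none of them.

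- A reader might infer that the check against the 900 mg cap, or the identification of overdose under Protocol 6.6, is compromised. The SAP plans no comparison of cream weights with the cap, and handling of an overdose during the trial does not use this derivation.
- A reader might infer that the error reaches the PK results, because the titles of Tables 4.1 to 4.3 say by actual dose. The SAP does not link that phrase to the weighed cream, and the listed parameters do not use a dose.
- A reader might infer that the exposure rules also contradict each other on what one weight record covers. The Table 1.14 footnote says "Daily Dose refers to the one lesion that either active or placebo treatment is applied to", whereas 11.3.2 spreads the day's total over every location ticked. Which reading applies depends on the eCRF, which is not among the documents. This is unsettled detail, not a demonstrated error, and it has no size that can be derived.

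**Conclusion.** The formula in SAP 11.3.2 is wrong as written. By the SAP's own definitions of A and B, B-A is the negative of the cream applied. The cumulative dose carries that sign into Table 1.14 and, by reference, into Listing 13.

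The size is a change of sign and nothing more. The conclusion rests only on the definitions of A and B and on the container losing mass when cream is used; the amounts in the illustration are not trial data. The primary safety conclusions and the secondary analyses do not depend on it. Severity: minor.

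**What to change.** In SAP 11.3.2, Extent of Exposure, replace B-A with A-B. The cumulative formula, Table 1.14 and Listing 13 can stay as they are, since they take their sign from that expression.

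The cost is one edit to one expression. Data collection, the eCRF weights and the statistical analyses do not change. If the displays have already been programmed, confirm that the code uses A-B so that program and SAP agree.
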